11.2 Period of observation

For the purpose of this trial, the period of observation for collection of AEs extends from signing of the informed consent form until the end of the trial (including follow-up period).

The investigator is not expected to actively monitor subjects for AEs once the clinical trial has ended. However, if the investigator becomes aware of a SAE in a subject after the end of the period of observation (regardless of the time elapsed from the trial end), and considers the event possibly related to prior trial treatment or procedures, the investigator should contact the Drug Safety department of Bionorica SE to determine how the AE should be documented and reported.

Regardless of the individual duration of the trial, any AE (including abnormal laboratory findings), irrespective of severity and whether serious or not, must be monitored by the investigator until it has satisfactorily subsided or has stabilized to such an extent that further marked improvement can no longer be expected or until a satisfactory medical explanation is found. The investigator must make every effort to contact subjects lost to follow-up. Attempts to contact such subjects must be documented in the subject's records (e.g., times and dates of attempted telephone contact, receipt for sending a registered letter).

This also applies to AEs still ongoing at the last visit of the individual patient. If necessary a further visit must be scheduled by the investigator.

It is the responsibility of the investigator to ensure that any necessary additional therapeutic measures and follow – up procedures are performed.

11.3 Assessment and recording of adverse events

The occurrence of AEs will be assessed by non-directive questioning of the subject at each visit. Further, AEs volunteered by the subject during or between visits or detected through observation, physical examination, laboratory test or other assessments will be documented. AEs that were ongoing at the end of the previous visit should be queried for resolution or change in severity or seriousness.

Clinical trial subjects will be instructed by the investigator to report any AEs, subjective complaints or objective changes in their well-being to the investigator or the clinic personnel, regardless of the perceived relationship between event and IMP.

All AEs (whether serious or non-serious, or considered as an alert term) must be documented.

In case of a **SAE** (refer to section 11.1.2), the investigator must additionally complete a 'SAE report form' at the time the SAE is detected. This form will be immediately send to the Drug Safety department of Bionorica SE as detailed in section □.

For each AE the following data will be recorded in the CRF:

- **Description of the AE** in medical terms (preferably: diagnosis), not as reported by subject.
Note: Every attempt should be made to describe the AE in terms of a diagnosis. If a clear diagnosis has been made, individual signs and symptoms will not be recorded unless they represent a typical or extreme manifestation of the diagnosis, in which case they should be reported as separate AE.
- Date of onset (start date) and date of recovery (stop date).
- **Intensity of the AE** as assessed by the investigator as follows:
 - **Mild:** The AE is easily tolerated and does not interfere with routine activities/ normal functioning of the subject.
 - **Moderate:** The AE causes discomfort and affects the subject's normal activities, i.e. interferes with routine activities, but are not hazardous, uncomfortable or embarrassing to the patient.
 - **Severe:** The AE causes considerable interference with the subject's usual activities, e.g. inability to work.
- **Causal relationship of the AE** to the IMP according to the available data as:
 - **Related:** There is a reasonable causal relationship, which means that there is evidence to suggest a causal relationship. The adverse event could medically (pharmacologically/ clinically) be attributed to the investigational product under trial in this protocol.
 - **Not related:** There is no reasonable causal relationship, which means that there is no evidence to suggest a causal relationship. The adverse event could not medically (pharmacologically/ clinically) be attributed to the investigational product under trial in this protocol.
- **Actions taken on the IMP:**
 - e.g. drug withdrawn, dose reduced, dose increased, dose not changed, permanently discontinued, temporarily discontinued and reintroduced, unknown, not applicable (e.g. AE occurred in IMP-free period)
- Other actions taken due to the AE:
 - e.g. corrective treatment
- **Outcome of the AE**, e.g.:
 - **Recovered/ resolved:** The AE had stopped completely and the stop date is recorded.
 - **Recovered/ resolved with sequelae:** No further changes are expected due to the AE and residual symptoms are assumed to persist.
 - **Not recovered/ not resolved:** The AE is ongoing; the event is followed up.
 - **Fatal:** The subject died as a consequence of the AE; date of death is recorded as stop date of the AE.
 - **Unknown:** Unknown to the investigator (e.g. patient lost to follow up).

- **Seriousness** according to definition in section 11.1.2.

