10.9.1 Procedure related risks

10.9.2 Risks related to the investigational medicinal product

Imupret® oral drops

The investigational products Imupret® oral drops contain the ingredients given in sections 0 and 8.3.2.

According to the Summaries of Product characteristics the following site effects and interactions may occur during intake:

Side effects

Rarely gastrointestinal disorders (e.g. abdominal pain, nausea, vomiting) may occur. Allergic reactions (e.g. rash, itching, dyspnea) may also occur.

When taken together with preparations containing matricaria flowers and also in patients with hypersensitivity to other plants of the Composite family (e.g. Yarrow herb (*Achillea Millefolium*)) allergic reactions may occur. In case of any undesirable side effects the use of the medicinal product should be discontinued and a doctor should be consulted.

Interactions with other medicines and other forms of interaction

No interactions with other medicines have been reported. When using preparations which contain oak bark, the resorption of alkaloids and other alkaline medicinal agents may be reduced or blocked if taken together.

Overdose

No cases of intoxication due to overdose has been reported.

Reference treatment

At the discretion of the investigator, Paracetamol as single doses up to 500 mg – not more than 3-4 times daily will be prescribed. Moreover, at the discretion of the investigator, topical treatment with e.g. benzydamine, lidocaine (in case of severe sore throat) may be prescribed. In

case an antibiotic treatment will be necessary, the investigator may prescribe e.g. amoxicillin clavulanate, cephytryaxons etc.

As it is not yet known, what kind of prescription will be exactly done by the investigator, possible side effects and interactions are hardly to be described in here in the protocol. In any case the investigator has to inform the patient and (or) his/her parent(s) about the risks related to the intake of Reference medication according to the respective Summaries of Product Characteristics.

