12.2.4 Safety evaluation

AEs will be evaluated considering frequency and intensity. Furthermore, AEs will be evaluated considering relationship to the IMP, outcome, and seriousness. Both will be described by absolute and relative frequency. Descriptive statistics will be calculated for clinical laboratory parameters determined. Frequencies of values inside and out of normal range (i.e. above and below) will be given where possible.

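### The Moderate adverse-event grade in protocol section 11.3 contradicts itself, so an uncomfortable event with some but not considerable interference has no consistent grade

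*Protocol*

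**What the plan says.** Protocol section 11.3 sets three intensity grades, assigned by the investigator.

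- **Mild:** "The AE is easily tolerated and does not interfere with routine activities".
- **Moderate:** "The AE causes discomfort and affects the subject's normal activities". An explanatory clause follows in the same sentence: "interferes with routine activities, but are not hazardous, uncomfortable or embarrassing to the patient".
- **Severe:** "The AE causes considerable interference with" the subject's usual activities. The one example given is being unable to work.

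The same section asks for AEs to be described as diagnoses where possible. Once a diagnosis is clear, "individual signs and symptoms will not be recorded unless they represent a typical or extreme manifestation of the diagnosis". Manifestations that meet that exception are to be reported as separate AEs.

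On use of the data, protocol section 12.2.4 states: "AEs will be evaluated considering frequency and intensity". Section 12.2 and the SAP's safety evaluation say the same. All three also list relationship to the product, outcome and seriousness, and all call for absolute and relative frequencies. None says whether events or patients are counted.

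**The concern.** The Moderate definition asks for discomfort and then denies it. The investigator has to decide which half to follow, and neither document says which. The reactions that protocol section 10.9.2 takes from the product information are of the affected kind: "Rarely gastrointestinal disorders (e.g. abdominal pain, nausea, vomiting) may occur". The two AEs with the oral drops described in section 6.2.1.2, vomiting and stomach ache, are of that kind too.

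At stake is the consistency of the intensity data. The trial is multicentre and open-label (section 8.1), and grading is left to the investigator. Different sites could resolve the contradiction differently, and they would do so knowing the treatment. Tolerability is part of the trial's title, and intensity is one of its planned AE summaries.

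The wording on typical manifestations raises a second, lesser question. Taken as it stands, it would have the ordinary symptoms of a diagnosis logged next to the diagnosis, which defeats the aim of recording a diagnosis.

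**Working it through.** The documents give no AE rate, count or severity distribution, so there is no figure to reproduce. The check sets the definitions side by side.

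**Intensity grades.** Take an event that causes discomfort and vary how far it interferes with activities:

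| Interference | Mild | Moderate | Severe | Result |
|---|---|---|---|---|
| None | Met if easily tolerated | Not met: no effect on activities | Not met | Mild |
| Some, not considerable | Not met: interferes | First half met, second half failed | Not met: not considerable | No consistent grade |
| Considerable | Not met: interferes | Second half failed | Met | Severe |

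The middle row is the gap. A child whose nausea or vomiting disturbs the day's routine without considerable interference belongs there. An event with some interference and no discomfort gives a strict reader the mirror-image difficulty: it meets the second half and fails the first. The uncomfortable case matters more, because it is the kind the protocol itself expects. No other section of the protocol, and nothing in the SAP, restates or corrects the scale.

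**Recording rule.** Three places bear on it:

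- Section 11.3, same note: the aim is to record a diagnosis in place of its component symptoms.
- Section 11.5: abnormal findings tied to a condition already documented are recorded separately only when the investigator judges them more severe than expected.
- Section 11.1.1: a pre-existing condition counts as an AE only if its course is atypical, with exacerbation or more frequent symptoms.

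All three fit *atypical or extreme*. None fits *typical or extreme*.

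**Illustration of the count, on an assumed number of symptoms.** If a diagnosis has k typical symptoms and each is logged as well as the diagnosis, the episode gives 1 + k records:

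- k = 1: 1 + 1 = 2 records
- k = 2: 1 + 2 = 3 records
- k = 3: 1 + 3 = 4 records

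The intended rule gives 1 record, so the event count for that one episode would be 2 to 4 times as large. The number of patients with at least one AE is 1 either way.

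**The case against.** The strongest reply is that the intended scale can be recovered. The grades already rise by interference: none, some, considerable. An investigator can use that order and ignore the stray clause. This stands in part. It shows that the defect is a contradictory clause and not a missing grade, and it shows what the correction should be. It does not show that every site would resolve the conflict in the same way.

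Several stronger readings are tempting, and the documents do not support them.

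- *Affected events would be pushed up to Severe.* Severe has its own criterion, considerable interference. An event below that level does not become severe because Moderate is badly worded.
- *Intensity and frequency are the whole of the safety evaluation.* The plan also covers relationship, outcome and seriousness, and the synopsis adds serious AEs, the incidence of adverse drug reactions and overall tolerability.
- *Serious-event reporting is compromised.* Section 11.1.2 says that seriousness, not severity, guides regulatory reporting.
- *The arms would be graded differently.* The wording is the same for both arms, and no between-arm test of AEs is specified. Open-label grading makes a difference possible, but nothing in the documents shows one.
- *The Severe example makes that grade unusable for children aged 6 to 12.* Inability to work is only an example. Replacing it would be polish.

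On the recording rule, the objection is stronger. The phrase may be *atypical* with a stray space, either in the source or from text extraction, and sections 11.1.1 and 11.5 point to that meaning. This half can therefore be no more than a wording check. Section 11.1.1 also says that worsening of common symptoms of the disease under study will generally not be recorded as an AE, which limits splitting for tonsillitis itself.

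**Conclusion.** The Moderate definition in section 11.3 is internally contradictory, and nothing else in the documents corrects it. On a literal reading, an uncomfortable event that interferes with activities, but not considerably, has no consistent grade. Intensity *could* be graded inconsistently across sites. That it *would* be depends on how investigators read the sentence, which the documents cannot settle.

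The reach is narrow. It covers the descriptive intensity tables for all AEs, whether or not they are related to the drug. The amount of misgrading cannot be calculated. Efficacy results, sample size, error rates and seriousness-based reporting are not touched.

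The point about typical manifestations is conditional on the source file. If the word really is *typical*, event-level counts could be inflated. The 2- to 4-fold figure is an illustration for one episode with one to three assumed symptoms, not an estimate for the trial. Counts of patients with at least one AE would not change.

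**What to change.** In section 11.3, delete from Moderate the final clause, from *but* onward, which rules out hazard, discomfort and embarrassment. Interference then separates the grades: none for Mild, some for Moderate, considerable for Severe.

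Check the source file for the phrase on typical manifestations. If it is not an extraction artefact, change *a typical* to *an atypical*, which brings it into line with section 11.5.

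The cost is one deletion and at most one changed word in the protocol, passed on to the sites. The SAP does not repeat the scale, so it needs no change for this point. No assessment, visit or sample-size figure changes.

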11.4 Reporting of SAE

Any SAE and AE that fulfil a reason for immediate reporting (as defined in section 11.1.4) will be reported immediately (within 24 hours after receipt) to the responsible ethics committee and authority according to the obligations of the Ukraine (online to State Expert Center MH).

Moreover, within 15 days after receipt by the investigator via telephone, fax or e-mail to the Drug Safety department of Bionorica SE:

Bionorica SE
Drug Safety
[contact]
[contact]
E-mail: [contact]

The initial report must be as complete as possible. The report should include at least the following information:

- **Clinical trial subject identification** (e.g. assigned subject number, age or year of birth, gender)
- **Identifiable reporting source** (e.g. centre number, name of investigator, telephone number, fax and/ or e-mail address)
- **Identification of the clinical trial** (e.g. trial code) or IMP
- **SAE term** (preferably: diagnosis; if possible, also including description and course of the SAE)
- **Seriousness criterion** (refer to section 11.1.2)
- **Causal relationship** between the occurrence of an AE and the administration of the IMP as assessed by the investigator according to the available data as defined in 10.2. If based on follow-up information the investigator changes his/her initial causality assessment, this should be submitted to the Drug Safety department of Bionorica SE immediately (i.e. within 24 hours after receipt) by using the SAE report form.
- **Signature of the investigator**

Following a report by phone, written information has to be sent by fax or e-mail to the Drug Safety department of Bionorica SE within two working days. When necessary an 'SAE Report Form' will be accompanied by relevant pages from the CRF, e.g. for medical history, AEs or concomitant medication (online-form in official site of State Expert Centre MH).

If the investigator does not have all information regarding an SAE, he/she will not wait to receive additional information before notifying the sponsor of the event and completing the 'SAE report form'. Information not available at the time of the initial report (e.g. an end date for the SAE or laboratory values received after the report) will be documented on a follow-up 'SAE report form' and reported within 15 days after receipt to the Drug Safety department of Bionorica SE.

Additional information not covered by an 'SAE Report Form', including copies of hospital reports, autopsy reports or other relevant documents, will be requested, if necessary, by either the monitor or the Drug Safety department of Bionorica SE for a detailed description and a final evaluation of the case. All personal identifiers (e.g. name, detailed birth of date) must be pseudonymized prior to submission by blinding personal data and using the assigned identification code of the subject.

The investigator should institute any supplementary investigations of SAE based on their clinical judgement of the likely causative factors. This may include seeking further opinion from a specialist in the field of the SAE. Bionorica SE may also request extra tests.

If the SAE information is incomplete or inconsistent and directly affects the sponsor's reporting obligation to health authorities, the Drug Safety department may directly contact the investigator for clarification.

The sponsor will be responsible for notification of the competent authorities, ethics committee(s) and investigators in the event of a SUSAR and any other important safety issues requiring expedited reporting, in accordance with the applicable legislation.

11.5 Abnormal laboratory parameters

Abnormal laboratory findings (e.g. clinical chemistry, haematology, or urinalysis) or other abnormal assessments (e.g. vital signs) will be judged by the investigator as 'clinically relevant' or 'not clinically relevant' based on the investigator's medical and scientific expertise. Abnormal, clinically relevant results should be verified to rule out laboratory error.

Clinically relevant, abnormal findings or other clinically relevant abnormal assessments that are detected during the clinical trial or that were present at baseline and significantly worsen during the trial will be recorded as AE. However, clinically relevant abnormal laboratory findings or other abnormal assessments that are associated with a medical condition already documented as medical history or AE will not be recorded separately, unless judged by the investigator as more severe than expected for the subject's condition.

If during treatment with an IMP abnormal laboratory findings occur which were not present at baseline and which were judged by the investigator as 'clinically relevant' and recorded as AE in the CRF, the investigator is responsible to carry out further clinical or laboratory tests until the values return to the normal range or until a plausible explanation is given by the investigator (e.g. disease).

11.6 Handling of pregnancies

The investigator will collect pregnancy information on any female subject, who becomes pregnant while participating in this clinical trial. The investigator will inform Bionorica about pregnancy department of Bionorica SE within 15 days after acknowledgment of a subject's pregnancy).

Any subject who becomes pregnant while participating in the trial should discontinue treatment and will be withdrawn from the trial.

The pregnancy must be followed up to determine outcome (including premature termination) and status of mother and child. Generally, follow-up will be no longer than 3 months following the estimated delivery date.

Newly diagnosed pregnancy in a clinical trial subject is not considered to be an AE or SAE unless meeting seriousness criteria, or it is suspected that the IMP interacted with a contraceptive method and led to pregnancy.

Pregnancy complications and elective terminations for medical reasons must be reported as an AE or SAE. Spontaneous abortions must be reported as an SAE.

Furthermore, any SAE occurring as in association with a pregnancy (in cases where the pregnancy occurred after the end of the trial participation of the subject) brought to the investigator's attention after the subject has completed the trial and considered by the investigator as reasonably related to the IMP must be promptly reported to the sponsor.

12 EVALUATIONS

12.1 Data Management

Data management comprises the following general processes in chronological order: Set-up of database, data entry and cleaning including query handling, coding procedures, data validation and final review of data.

Upon receipt of CRFs and respective raw data sheets, the data from the CRFs will be entered and transferred into the trial data base. Data base will be prepared for data entry and will reflect the final version of the CRF and raw data sheets. Adequate quality control methods will be applied. Identified discrepancies, will be queried by a responsible data manager using data clarification forms and forwarded to the investigator. Data sets and data base will be hard locked after all discrepancies are resolved and the analysis sets of subjects are documented. In case, that the data base has to be opened, this will be done only after agreement with all involved parties. All changes after data base hard lock will be tracked. All clinical data included in the data base will at least be listed.

For data coding (e.g. AEs, medical / surgical history, medication) internationally recognized and accepted dictionaries will be used (Medical Dictionary for Regulatory Activities (MedDRA) for AEs and WHO-dictionary for medication). In general, the latest version of medical dictionaries valid at data base setup will be used for coding throughout the clinical trial.

12.2 Statistical evaluation

The statistical planning of the trial and the statistical analyses will be conducted following the principles specified in the ICH Topic E9 (ICH, 1998), and will be carried out by a qualified statistician in accordance with the ICH. Technical details of the statistical analyses will be specified prior to data analyses.

In general, there will be one main statistical evaluation.

Data base will be closed after all data are entered and cleaned.

In general, unless otherwise stated, continuous data will be summarized by means of descriptive statistics (mean, standard deviation (SD), median, quartiles, minimum, and maximum). Categorical variables will be described in contingency tables as absolute number and percentages.

AEs will be evaluated considering frequency and intensity. Furthermore, AEs will be evaluated considering relationship to the IMP, outcome, and seriousness. Both will be described by absolute and relative frequency. Descriptive statistics will be calculated for clinical laboratory parameters determined. Frequencies of values inside and out of normal range (i.e. above and below) will be given where possible.

This is an exploratory trial with no formal sample size estimation. Therefore, beneath descriptive statistics of efficacy endpoints, concluding statistics may be performed in a data driven way, in order to find clinically relevant differences between study participants, time points and treatments. Possible corrections to prevent an alpha inflation will be performed, if meaningful.

Specifications of the biometrical evaluation will be defined after all data management processes of the study phase will be terminated and data base was closed. In general, variables will be analyzed considering the underlying analysis set, treatment and time point, if meaningful.

